7.2 Study Termination

Patients may withdraw from the study at any time, of their own choice or by investigator decision, due to safety reasons or in case the patient is not able to comply with the protocol. Data collected up to the end of follow-up will be used in the final analysis of the study. If a patient wants to discontinue the study participation, data collected until that time point will be analysed in the study.

Early termination of the study may occur due to decision of regulatory authority or ethics committee, safety issues or sponsor decision. The study is completed when the last patient has done their last study visit.

8 STUDY MEDICATION

8.1 Study medication

Rituximab/MabThera®

MabThera 1000 mg concentrate for solution for infusion, 100 ml.

Active substance: Rituximab

ATC-code: L01XC02

Rituximab is a sterile, clear, colourless, preservative-free liquid concentrate designed for intravenous administration. The product is supplied at a concentration of 10 mg/mL in 500-mg (50-mL) single-use vials. Rituximab is formulated for intravenous administration in sodium chloride 9 mg/mL, sodium citrate dihydrate 7.35 mg/mL, polysorbate-80 0.7 mg/mL, and sterile water for infusion. The pH is adjusted to 6.5.

8.2 Administration of study drugs

A MabThera dose of 1000 mg will be given as intra-venous infusion in 1000 ml physiological saline (0.9 %, any brand provided by the pharmacy). Before administration of MabThera all patients will be given pre-medication to prevent or reduce possible side effects from MabThera.

Premedication is delivered 1-2 hours prior to rituximab and consists of T. Paracetamol 1000 mg, T. Loratadine 10 mg and T. Betapred (Betamethasone) 0.5 mg x 12 p.o (dissolved in a glass of water) in order to reduce the incidence of infusion-related reactions.

Patients remain on their stabilized treatments with psychotropic drugs during the first phase (20 weeks) of the study.

MabThera will be administered on one single occasion.

The MabThera treatment is administrated at the Rheumatology clinic at Örebro University Hospital. Study staff at the department of Rheumatology will prepare the saline bag for each patient infusion, adding MabThera. All bags will be labelled with a study specific label (**Error! Reference source not found.**). Each bag for infusion will be prepared just in time for each visit.

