Although the experience with immunomodulatory drugs such as corticosteroids, intravenous immunoglobulin (IVIG) and methotrexate is longer, as compared to rituximab, they have drawbacks: Corticosteroids strongly increase the risk for mania in psychiatric patients, which may further impair psychiatric health; IVIG is a blood-derived product, which makes its availability limited and furthermore, according to experience with patients with PANS, monthly treatments are often required to keep the patient symptom free. This makes IVIG costly and complicated. Trials with methotrexate on psychiatric populations have not yet been published, but we anticipate that psychiatric patients are reluctant towards a weekly intake of chemotherapy. Mycophenolate mofetil and azathioprine are other similar options used in autoimmune encephalitis and other autoimmune disorders, but not as far as we are aware, for psychiatric disorders. A fourth option is adding the antibiotic minocycline, which has anti-inflammatory properties, but minocycline must be dosed twice daily, which may affect compliance. Finally, since rituximab is regarded as sufficiently safe in large populations suffering from autoimmune disorders, thus we expect it to be likewise safe in psychiatric patients. Interestingly, a prevailing opinion on the mechanism of IVIG (hitherto the best immunomodulator in PANS treatment) is its modulation of B-cell function (63) which is also the main mechanism of rituximab). Accordingly, we expect the presumed benefits of rituximab to overrun the possible harm caused by this drug in markedly ill psychiatric patients with SSD.

Our experience of the treatment and the patient group

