9 ADVERSE EVENT, AE AND SERIOUS ADVERSE EVENT, SAE

9.1 Adverse Events, AE

An Adverse Event (AE) is any untoward medical occurrence in a patient/healthy volunteer administered a pharmaceutical product and which does not necessarily have to have a causal relationship with that treatment or usage. An AE can therefore be any unfavourable and unintended sign (including an abnormal laboratory finding), symptom or disease temporally associated with the use of a medical (investigational) product, whether or not related to the product.

Patients will be asked if they have experienced any AE by means of the following questions, administered at each visit:

- Have you noticed any new symptoms or problems since your last visit? If yes, which?
- Do you gather these symptoms can be related to a rituximab treatment?
- Have you noticed if any of your previous side effects have attenuated or increased? If yes, which ones?

We will also ask questions on specific adverse events that have been documented to be associated with rituximab treatment at each visit using the AAR. In addition, specific AEs, relevant for psychiatry, will be checked with the UKU Side Effect Rating Scale at **endpoint 1 and 2**.

The sponsor, as principal investigator or any investigator delegated to work in the study will record any AEs and assess the seriousness and severity (mild, moderate, severe) and whether the AE is related to the study medication. All investigators delegated to work in the study will report AEs to the principal investigator who is the sponsor in this study.

All AEs that are observed from the time of the administration of study medication until the patient leaves the study will be registered, analysed and summarized at the end of the study. Only serious adverse events will be recorded in the medical record.

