The side effects of rituximab include infusion reactions, severe skin and mouth reactions, hepatitis B virus reactivation and in extremely rare cases (1/25000 in patients with rheumatoid arthritis (102), progressive multifocal leukoencephalopathy (PML), a serious brain infection caused by the JC virus. We will collaborate with a senior rheumatologist who is experienced with rituximab. Since the treatment may activate latent infections, all patients will be screened for hepatitis and HIV prior to the study. The patients will be pre-medicated to reduce the risk of infusion-related side effects, and they are carefully monitored during the course of the study.

The reason to not use a standard drug for inflammation, such as cortisone, is because it may induce mania in susceptible individuals and is therefore not suitable for psychiatric patients.

We will film the patients on three different occasions. This is because we want to be able to show the patient if there is a treatment effect or not. It may also enable a completely external assessment of treatment effects. Since rituximab has not been tested in trials of psychiatric disorder an effect of the drug can be questioned. In such case we possibly could show video clips of treatment effects, if the patient allows it (but this is not included in this study). The film clips may also support a request for further treatment with the drug.

Early onset of severe psychiatric disability is associated with a particularly poor long-term prognosis. This is often the case for schizophrenia. Delayed treatment may cause persistent brain damage if associated with inflammation in the brain (which is presumed). We believe that earlier treatments may have better effects on the symptoms than treatment that are first provided after many years with the disease. Also, rituximab is frequently used for treating children and adolescents with MS (103). Thus it would be unjust to exclude them from participation in a trial with a medication that may prove helpful.

The patients will remain on their standard psychiatric treatment throughout the course of the study and are allowed to adapt their medication dose accordingly. Therefore, we do not put the patient's mental health at risk. The side effects of rituximab do not coincide with those that can be expected from psychiatric medication (apart from possibly clozapine), which implies low risk for add-on side effects.

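### Section 12.3 calls cortisone unsuitable for psychiatric patients, yet every patient takes betamethasone before the infusion; the risk assessment omits it and adverse-event recording cannot attribute an event to it

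*Combined protocol and SAP*

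**What the plan says.** On corticosteroids in this population:

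- Section 4.1, comparing candidate immunomodulatory drugs: "Corticosteroids strongly increase the risk for mania in psychiatric patients, which may further impair psychiatric health".
- Section 12.3, on why a standard anti-inflammatory drug such as cortisone is not used: "it may induce mania in susceptible individuals and is therefore not suitable for psychiatric patients".

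On what patients receive (section 8.2):

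- "Before administration of MabThera all patients will be given pre-medication to prevent or reduce possible side effects from MabThera".
- The premedication is paracetamol, loratadine and "T. Betapred (Betamethasone) 0.5 mg x 12 p.o (dissolved in a glass of water", taken 1–2 hours before rituximab. Section 7.1 allows this at home or at the clinic.

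On the risk of the premedication, section 12.3 says only this: "The patients will be pre-medicated to reduce the risk of infusion-related side effects". The psychiatric side effects it discusses, depression and nervousness, are listed for rituximab.

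On recording and attribution (section 9.1):

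- An open question about new symptoms is put at each visit.
- The patient is then asked "Do you gather these symptoms can be related to a rituximab treatment".
- The AAR covers events known to be associated with rituximab.
- The investigator assesses "whether the AE is related to the study medication".
- Registration of adverse events begins when the study medication is administered.

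**The concern.** The section that weighs risk against benefit uses mania as its reason to reject a corticosteroid. It does not say that every participant will take one. A reader of 12.3 alone, such as an ethics committee member, would not learn this.

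The second problem is attribution. Safety and tolerability of rituximab is a stated objective (section 5.1). If a patient becomes elated, agitated or sleepless soon after the infusion day, two drugs given within hours of each other are candidate causes, and the protocol itself links one of them to mania. The recording scheme offers rituximab or study medication as the cause, and nothing for the premedication. The trial is open and single-arm, so no group receiving the premedication without rituximab exists to separate the two. At stake are the causality column of a 12-patient safety table and the completeness of the stated risk-benefit balance.

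**Working it through.** The plan gives no figure to reproduce on this point, so the check is mainly of text, with three short calculations.

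**Do the sections conflict?** Section 4.1 and section 12.3 both discuss the choice of anti-inflammatory treatment, whereas 8.2 concerns one premedication intake. Section 12.3, however, draws its conclusion for psychiatric patients in general, with no limit on dose, duration or purpose. No section says that a single premedication intake is a different matter. The wording therefore conflicts, and the distinction that might resolve it is not written down.

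**Does 12.3 cover the premedication?** It mentions it once, as a means of lowering infusion risk. Neither betamethasone nor any effect of it appears.

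**Can an event be attributed to the premedication?**

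- Patient question: rituximab only.
- AAR: events associated with rituximab. Its items are not shown.
- Investigator: relation to the study medication. Section 8.1 identifies this as rituximab, and section 8.3 lists MabThera and saline as the study drug. The premedication appears in neither. The plural in the title of 8.2 leaves slight room to include it, so the term is at best ambiguous.
- Start of registration: at study medication, 1–2 hours after the steroid. That interval falls outside registration.

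**When is the first safety contact after the infusion day?** Table 1 has no week 1 row; its first later contact is the week 2 nurse check-up, with side-effect questions and the AAR. The Table 2 header has week 1 as visit 3 and week 2 as visit 4, and section 7.1.4.3 also calls week 2 visit 4. Whether week 1 is a real contact, and what is asked there, cannot be settled from these documents.

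**Arithmetic.**

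- Exposure: 0.5 mg × 12 = 6 mg per patient, in 12 of 12 planned patients.
- Weight of one event: 1/12 = 8.3 percentage points of the proportion of patients with an event rated related to rituximab.
- Chance of at least one steroid reaction among 12 patients: 1 − (1 − p)^12. The documents give no p, so these rates are assumptions:

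| Assumed rate p | Chance of at least one in 12 |
|---|---|
| 0.5% | 5.8% |
| 1% | 11.4% |
| 2% | 21.5% |
| 5% | 46.0% |
| 10% | 71.8% |
| 20% | 93.1% |

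For example, at 5%: 1 − 0.95^12 = 0.460. The range is too wide to say whether such an event is likely in this trial.

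**The case against.** The strongest reply is that 4.1 and 12.3 explain why steroids were not chosen as the treatment, while 8.2 is one intake to prevent infusion reactions. That stands. A reader might infer that the protocol breaks its own rule by giving betamethasone; the documents do not support this, because no section prohibits steroid premedication. What remains is an unqualified sentence in 12.3 that needs to be squared with 8.2.

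A reader might also infer that a steroid reaction will be missed or will be booked as a rituximab reaction. That goes too far:

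- Section 9.1 defines adverse events without regard to cause and asks openly about new symptoms at each visit.
- A nurse attends the infusion, the patient is not left alone for an hour afterwards, and regular psychiatric visits continue (7.1).
- The AAR items and the supplementary infusion routine cited in 7.1 are not available, so they may already ask about related symptoms.
- The absence of scheduled clinician psychiatric ratings between week 0 and week 12 concerns efficacy scales. It does not show that adverse events go uncollected.

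Nor is it a wrong answer if the investigator rates a steroid reaction as unrelated to rituximab: for an objective about rituximab, that is the correct rating. The remaining fault is that the actual cause has no place on the form.

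Finally, 8.3 points is the weight of any single event in 12 patients, and no endpoint or decision rule changes. That is fair, and it is why this is a low-cost improvement to safety recording and no threat to the primary analysis.

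**Conclusion.** The point holds in a limited form. Sections 4.1, 8.2 and 12.3 are not reconciled, and 12.3 omits a drug that all 12 patients are due to take. The scheme in 9.1 starts registration 1–2 hours after that drug and provides no way to name it as a cause. An early mood or agitation event can therefore be attributed to rituximab, or recorded with no cause, and the single-arm design cannot correct this afterwards.

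The size is one event = 8.3 percentage points of the rituximab-related proportion. How probable such an event is remains unknown. The conclusion assumes that study medication means rituximab, as 8.1 and 8.3 indicate, and that the documents not available here contain no separate attribution step. It implies no view on whether the premedication is appropriate.

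**What to change.** 1. Reconcile sections 4.1, 8.2 and 12.3, and cover the premedication, including the steroid, in the risk assessment in 12.3. The choice of premedication stays with the clinical team.
2. In 9.1, start adverse-event registration when the premedication is taken.
3. In 9.1 and the CRF, record causality separately for rituximab and for the premedication, and state what study medication covers.
4. Ask about mood elevation, agitation and sleep at the first scheduled contact after the infusion. First clarify whether that is the week 1 visit in the Table 2 header or the week 2 nurse check-up in Table 1.

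Cost: protocol wording, one CRF field and three questions at an existing visit. No extra patients, visits or analyses are needed.

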8.3 Storage and preparation of study medication

All study drug, MabThera and saline for dilution, will be available at the department of Rheumatology at Örebro University hospital.

9 ADVERSE EVENT, AE AND SERIOUS ADVERSE EVENT, SAE

9.1 Adverse Events, AE

An Adverse Event (AE) is any untoward medical occurrence in a patient/healthy volunteer administered a pharmaceutical product and which does not necessarily have to have a causal relationship with that treatment or usage. An AE can therefore be any unfavourable and unintended sign (including an abnormal laboratory finding), symptom or disease temporally associated with the use of a medical (investigational) product, whether or not related to the product.

Patients will be asked if they have experienced any AE by means of the following questions, administered at each visit:

- Have you noticed any new symptoms or problems since your last visit? If yes, which?
- Do you gather these symptoms can be related to a rituximab treatment?
- Have you noticed if any of your previous side effects have attenuated or increased? If yes, which ones?

We will also ask questions on specific adverse events that have been documented to be associated with rituximab treatment at each visit using the AAR. In addition, specific AEs, relevant for psychiatry, will be checked with the UKU Side Effect Rating Scale at **endpoint 1 and 2**.

The sponsor, as principal investigator or any investigator delegated to work in the study will record any AEs and assess the seriousness and severity (mild, moderate, severe) and whether the AE is related to the study medication. All investigators delegated to work in the study will report AEs to the principal investigator who is the sponsor in this study.

All AEs that are observed from the time of the administration of study medication until the patient leaves the study will be registered, analysed and summarized at the end of the study. Only serious adverse events will be recorded in the medical record.

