7 STUDY PLAN AND DESIGN

7.1 Study outline

After a screening visit, patients who meet the inclusion criteria will be asked to participate in this study. Plasma drug levels of the on-going medication will be measured before inclusion. Patients will be allocated to treatment with rituximab. If the patient is treated with anti-hypertensive drugs these shall be withdrawn 12 hours prior to rituximab treatment. Patients will receive the premedication 1-2 h prior to rituximab in their home or at the clinic. A nurse, experienced with rituximab treatment, will accompany the patient during the hours of rituximab infusion. Blood pressure will be measured before and after treatment and at every change of the speed of the infusion. The temperature will be measured before and after treatment. Mabthera will be administered according to the guidelines for safety of the patients, see supplementary file "*Rutiner för behandling med Mabthera inom ramen för studierna RITS-PO och RITS-PS*". Patients will rest for an hour after the termination of the infusion and will not be left alone during this time.

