All patients will be treated with the study drug rituximab on one single occasion and followed for a total of 1 year. They will have a total of 13 visits (screening prior to inclusion can be divided into more than one visit if necessary) with a clinician or research nurse who is experienced with rituximab and with psychiatric patients. An extensive psychiatric interview will be performed with each patient and his/her next of kin at baseline. We will also review medical records in order to document previous symptomatology and treatment trials. A short video recording is optional. All participants will be examined for psychiatric, neurological and motor symptoms, cognitive functioning, and a range of biomarkers. However only blood sampling and the interview are prerequisites for participation, all other examinations and tests are optional. Prior and post treatment the optional lumbar puncture and fMRI will be performed for further diagnostic evaluation and assessment of blood-brain barrier function. Faeces samples will also be collected prior to treatment and endpoint 1 of this study (optional) as well as gut biopsy prior to treatment (optional). Patients are requested to remain on their standard psychiatric treatment until endpoint 1, and treatment should be stable for the last 1 month prior to baseline. Patients are allowed adaption of their on-going psychiatric treatments after week 20 but also earlier if the treating physician deems this necessary.

Biological and psychiatric assessments will be performed at pre-decided time points (see table 1). Patients will be followed by additional visits to a nurse for in-between visits.

Side effects will be monitored at each visit. Patients will continue their regular visits with the psychiatric staff.

At endpoint 1 (20 weeks) a separate interview lasting approximately 45 minutes will be held for a qualitative analysis.

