7.1.4.8 Qualitative content analysis

The 12 participants from the study will be interviewed about their experiences about participating in the study, using a semi structured interview guide. The questions will be focusing on the participants' experiences about the treatment, the approach from the staff their feelings about their psychiatric diagnosis. Our hypothesis is that the patients may have other thought about their psychiatric condition as it now can be viewed as an inflammatory disorder instead of purely a mental condition. Also we are interested in if the participants have reflected on any change in the approach of the staff since they now are regarded as “somatically ill patients” not simply “psychiatric patients”. The interviews will be transcribed verbatim and analyzed with qualitative content analysis.

Table 1 Study plan

Week		
-4 – 0	Screening prior to treatment with rituximab Decision on inclusion / exclusion	
 • Evaluation of suitability • Vaccination check up (+varicella) • Information to not use attenuated vaccines, what risks are involved and signs of immunosuppression • Consent form • Information card about drug study participation • Demographics questionnaire including FTF-Brief • Treatment history • PNISSI and fine motor examination • Physical examination • Check anti-hypertensive medication* • Test for group A streptococcus • Blood sample • Routine safety: Test of hepatitis, HIV, TB and routine tests • Therapeutic drug monitoring • Urine: illicit drug screen and pregnancy test, inflammatory markers • Assessments (CGI-S and MINI, psychiatric rating scales, GAF, EQ-5D, Level 1 Cross-cutting symptom measure of global symptom severity) • Functioning: PSP and BBQ • Side-effects, AAR • UKU • Client satisfaction questionnaire (CSQ) • Cognitive tests Video recording I • Lumbar puncture (optional) • Faeces biopsy and sample (optional) • fMRI (optional)
0	Baseline Rituximab dose 1000 mg	
 • Assessments (PANSS, CGI-I**, PGE, CGI-S) • Blood sample (inflammatory markers)
2	Nurse check-up	
 • Side-effects, AAR
5, (+/- 1 week)		
 • Side-effects, AAR • Patient evaluated improvement (PGE) • Blood sample (B-cell population)
8	Nurse check-up	
 • Side-effects, AAR • Patient evaluated improvement (PGE)

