9.2 Serious Adverse Event, SAE

Each adverse event is to be classified by the investigator as serious or non-serious. An adverse event that meets one or more of the following criteria/outcomes is classified as serious:

- Results in death
- Is life-threatening, i.e., the patient was, in the opinion of the Investigator, at immediate risk of death from the event as it occurred (It does not include an event that, had it occurred in a more severe form, might have caused death.)
- Results in persistent or significant disability/incapacity
- Requires in-patient hospitalization or prolongs hospitalization
- Is a congenital anomaly/birth defect
- Is another medically significant event that, based upon appropriate medical judgment, may jeopardize the volunteer and may require medical or surgical intervention to prevent one of the outcomes listed above (e.g., allergic bronchospasm requiring intensive treatment in an emergency room or home, blood dyscrasias or convulsions that do not result in hospitalization, or the development of drug dependency or drug abuse)

SAE that occurs during the study will be documented and reported to sponsor within 24 hours after the investigator is aware of the SAE. SAEs will be documented, analysed and summarized at the end of the trial. SAE will be followed until the participation in the trial is ended or they are resolved.

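### Non-serious adverse events that begin and resolve between consent and the infusion are not registered, and the AE window in 9.1 differs from the SAE window in 9.2

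*Combined protocol and SAP*

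**What the plan says.** Section 9.1 fixes the registration window for adverse events: "All AEs that are observed from the time of the administration of study medication until the patient leaves the study will be registered". The same sentence makes registration the route into the end-of-study analysis and summary. Section 8.1 names the study medication as rituximab/MabThera, and 8.3 reads "All study drug, MabThera and saline for dilution, will be available at the department of Rheumatology". Premedication is not listed as study drug.

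Section 9.2 uses a different window for serious events: "SAE that occurs during the study will be documented and reported to sponsor within 24 hours", and "SAEs will be documented, analysed and summarized at the end of the trial". It sets no start point at the infusion.

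Several study-driven exposures come before the infusion:

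- Section 7.1: "Prior and post treatment the optional lumbar puncture and fMRI will be performed". Table 1 lists the first puncture at screening (weeks -4 to 0) and the second at week 20.
- Section 7.1 also places the optional gut biopsy before treatment only.
- For patients on blood-pressure drugs, 7.1 states: "If the patient is treated with anti-hypertensive drugs these shall be withdrawn 12 hours prior to rituximab treatment".
- For all patients, 8.2 states: "Premedication is delivered 1-2 hours prior to rituximab".

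Sections 7.1, 7.1.2 and 9.1 say that side effects are asked about at every visit. Tables 1 and 2 mark the side-effect check and AAR at screening and then from week 2, with no mark at the week 0 infusion visit. UKU is marked at screening, week 20 and week 40.

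**The concern.** The first lumbar puncture and the gut biopsy are optional invasive procedures done for the study, and they fall before the window opens. Section 12.3 expects lumbar puncture pain to be brief and the gut examination to be free of pain and danger. Brief events are the ones most likely to be over before dosing, so under 9.1 the trial would not register the non-serious events needed to check those statements for the pre-treatment procedures.

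The rituximab summary is touched in a second way. Entry to the AE record depends on when an event is observed, and 9.1 does not ask whether onset was before or after the infusion. Relatedness is judged only against the study medication. A symptom that started after a pre-treatment procedure and is still present after dosing can thus be counted as a post-rituximab event. In 12 patients a few misdated events are visible in a frequency table, and the synopsis makes frequency, seriousness and severity of side effects a secondary outcome.

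**Working it through.** The plan states no AE rate or count for this period, so there is no figure to reproduce. The check places each exposure on the timeline against the two windows.

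| Exposure | Who | Timing | Non-serious event over before infusion | Event present or appearing once infusion starts |
|---|---|---|---|---|
| Lumbar puncture, first | optional | weeks -4 to 0 | not registered | registered |
| Lumbar puncture, second | optional | week 20 | not applicable | registered |
| Gut biopsy | optional | before treatment only | not registered | registered |
| Antihypertensive withdrawal | only patients on these drugs | 12 h before | not registered | registered |
| Premedication | all patients | 1-2 h before | not registered | registered |

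So 1 of 2 lumbar punctures and 1 of 1 gut biopsies precede the AE window. The last two rows matter less: the interval before the infusion is 12 hours at most, and blood pressure is measured before, during and after the infusion (7.1), so many of these effects would be seen inside the window.

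**Serious events.** The wording of 9.2 includes an SAE before the infusion. However, 9.1 defines an AE as occurring in a patient who has been given a pharmaceutical product, and an SAE is a subset of AEs. Read together, the two sections leave it unclear whether a hospitalisation after a screening lumbar puncture counts.

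**Pre-dose reference.** AAR, the open side-effect questions and UKU are recorded at screening. The protocol does not say that these answers enter the AE summary or serve as the comparison for later reports, and 9.1 mentions UKU only at endpoints 1 and 2. With no side-effect check marked at week 0, the last scheduled record can be up to 4 weeks old at dosing.

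**Illustration of scale only.** Let p be an assumed per-patient risk of a non-serious event that resolves before the infusion; the documents give none. With n patients exposed, the chance of at least one unregistered event is 1 - (1 - p)^n and the expected number is np. Here n = 12 means that everyone is exposed, and n = 6 assumes that half accept an optional procedure.

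| p | n = 12: chance | n = 12: expected | n = 6: chance | n = 6: expected |
|---|---|---|---|---|
| 2% | 21.5% | 0.24 | 11.4% | 0.12 |
| 5% | 46.0% | 0.6 | 26.5% | 0.3 |
| 10% | 71.8% | 1.2 | 46.9% | 0.6 |
| 20% | 93.1% | 2.4 | 73.8% | 1.2 |
| 30% | 98.6% | 3.6 | 88.2% | 1.8 |

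For example, 1 - 0.95^12 = 0.460. The range is wide because p is unknown; the table does not estimate what will be missed.

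**The case against.** The strongest defence is that the safety objective in 5.1 concerns rituximab, not the burden of study procedures, and that a window opening at administration suits the AE definition in 9.1. That stands as far as it goes: the main rituximab summary would change little.

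The defence also has good answers to several stronger readings:

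- A reader might infer that there is no pre-dose reference. There is one: AAR, the open questions and the 48-item UKU are all scheduled at screening, and the same instruments are used after dosing.
- A reader might infer that 9.1 discards the screening answers. It does not say so. The protocol is silent on their use, and silence is not exclusion.
- A reader might infer that all harms before the infusion are lost. Serious events are covered by the wording of 9.2, and events that persist or first appear once the infusion starts are inside the 9.1 window.
- A reader might infer that all 12 patients are affected for up to 4 weeks. Lumbar puncture and biopsy are optional, and the withdrawal applies only to patients on those drugs. Of the four exposures, only the premedication reaches everyone, for 1-2 hours.

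The visit questions also ask about new symptoms since the last visit and about changes in earlier side effects, which helps separate old from new. This reduces the misdating risk but does not remove it, because onset relative to the infusion is not recorded and no check is marked at week 0.

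**Conclusion.** The point holds in a limited form. By a stated rule in 9.1, non-serious events confined to the period between consent and infusion are not registered, analysed or summarised; the first lumbar puncture and the gut biopsy are the main sources. Sections 9.1 and 9.2 use different windows and should be aligned. Events that began earlier and persist can enter the record without a mark that they preceded dosing. The text and Tables 1 and 2 also disagree on a side-effect check at week 0.

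The expected effect on the rituximab safety result is small. The number of missed events cannot be computed, since it depends on the uptake of optional procedures and on event rates that the documents do not give. The conclusion assumes that study medication in 9.1 means MabThera, as 8.1 and 8.3 indicate, and not the premedication. If premedication were counted, the window would open 1-2 hours earlier, and the lumbar puncture and biopsy would still precede it. This is a cheap improvement to safety recording and does not invalidate the safety analysis.

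**What to change.** 1. In 9.1, start AE registration at signed consent, in line with the study-wide SAE window in 9.2. Word the AE definition so that it clearly includes events before the infusion.
2. For each AE, record whether onset was before or after the start of the infusion, and whether it is related to a study procedure.
3. Report the two periods separately. Base rituximab tolerability on events with post-infusion onset, and state that these are read against the screening AAR and UKU.
4. Reconcile Tables 1 and 2 with the text on whether side effects are asked about at week 0.

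The cost is a few sentences, two extra fields on the AE form and slightly more recording work. The side-effect questions are already asked at screening.
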